4. STUDY OBJECTIVES AND ENDPOINTS

Primary Objective	Primary Endpoint
To evaluate the efficacy of BIIB122 225 mg compared with placebo, based on the time to confirmed worsening in MDS-UPDRS Parts II and III combined score	Time to confirmed worsening in MDS-UPDRS Parts II and III over the treatment period (minimum 96 weeks and maximum 180 weeks)
Secondary Objectives	Secondary Endpoints
To evaluate the safety and tolerability of BIIB122 225 mg compared with placebo when administered for 96 to 180 weeks	Incidence of AEs and SAEs
To evaluate the efficacy of BIIB122 225 mg compared with placebo, based on the time to confirmed worsening in MDS-UPDRS Part II score	Time to confirmed worsening in MDS-UPDRS Part II score over the treatment period
To evaluate the efficacy of BIIB122 225 mg compared with placebo, based on change in the MDS-UPDRS Parts II and III combined score, when administered for 96 weeks	Change in MDS-UPDRS Parts II and III combined score from Baseline to Week 96
To evaluate the efficacy of BIIB122 225 mg compared with placebo, based on change in mSE-ADL score	Time to confirmed worsening in mSE-ADL score over the treatment period
To evaluate the efficacy of BIIB122 225 mg compared with placebo, based on change in MDS-UPDRS Parts I, II, and III combined score	Change in MDS-UPDRS Parts I, II, and III combined score from Baseline to Week 96

[figure not shown]
CONFIDENTIAL

The information contained herein may not be used, disclosed, or published without the written consent of
Biogen MA Inc.

CONFIDENTIAL

The information contained herein may not be used, disclosed, or published without the written consent of
Biogen MA Inc.

CONFIDENTIAL

The information contained herein may not be used, disclosed, or published without the written consent of
Biogen MA Inc.

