Sample Size Determination: A minimum of approximately [REDACTED] events would be required to detect a [REDACTED] relative treatment effect for BIIB122 [REDACTED] for the primary endpoint with [REDACTED] power, at the 2-sided significance level of [REDACTED]. Up to 2 potential interim efficacy analyses, pending regulatory feedback, may be conducted in which case approximately [REDACTED] events would be needed to achieve approximately [REDACTED] power for the study. With a sample size of approximately [REDACTED] participants per treatment group, followed for a minimum of [REDACTED] weeks ([REDACTED] weeks of treatment followed by [REDACTED] weeks of SFU) and a maximum of

CONFIDENTIAL

The information contained herein may not be used, disclosed, or published without the written consent of Biogen MA Inc.

█ weeks (█ weeks of treatment followed by █ weeks of SFU), a total number of up to █ events is expected to have been reached when all participants complete the planned treatment period and provides the study with approximately █ power with 2 potential IAs. These estimates assume a median time to confirmed worsening of █ weeks (approximately █ months) in the placebo group, and a █ annual exponential dropout/censoring rate.

Visit Schedule:

Study assessments conducted at each visit are listed in the Schedule of Activities ([Table 1](#)).

Duration of Study Participation:

The total study duration for each participant (including the Screening period) will be a minimum of approximately 103 weeks and a maximum of approximately 187 weeks as follows:

- 5-week Screening period █
- 96-week minimum to 180-week maximum (when the total number of events for the primary endpoint reaches approximately 200 events) double-blind, placebo-controlled treatment period
- █

Benefit-Risk Analysis:

There is a significant need for an effective disease modifying therapy that delays PD progression, which is not addressed by current therapies. Lysosomal dysfunction contributes to disease risk in PD patients, suggesting that therapeutics that reduce LRRK2 kinase activity may provide benefit for patients with PD.

The data from previous clinical studies with doses of up to 300 mg QD in participants with PD (28 days exposure), and up to 400 mg BID in healthy volunteers (14 days exposure)

CONFIDENTIAL

The information contained herein may not be used, disclosed, or published without the written consent of Biogen MA Inc.

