5. STUDY DESIGN

5.1. Study Overview

This Phase 3, multicenter, randomized, double-blind, placebo-controlled, parallel-group study is designed to evaluate the efficacy and safety of BIIB122 in approximately 400 participants with LRRK2-PD who are in the early stage of the disease. The study will be conducted at approximately 55 study sites globally. The study population is defined as participants with a clinical diagnosis of PD within 5 years of the Screening Visit, a mHY 1-2.5 (in OFF state), who carry a pathogenic variant in the LRRK2 gene (e.g., *G2019S*, *N1437H*, *R1441G*, *R1441C*, *R1441H*, *Y1699C*, or *I2020T*).

Randomization will be performed using IRT. Participants will be randomly assigned to receive BIIB122 225 mg or placebo orally QD in a 1:1 ratio. [REDACTED]

[REDACTED]

The double-blind placebo-controlled treatment period is a minimum of [REDACTED] weeks and could be as long as [REDACTED] weeks for each participant. The study duration depends on when the last enrolled participant has completed the [REDACTED] Visit and number of events for the primary endpoint reaches a minimum number to provide approximately [REDACTED] power for the study, which will be specified in the SAP, since the minimum number depends on the number, timing, and nature of planned interim analyses. Each participant will have a SFU Visit 2 weeks after the last dose. The majority of in-clinic visits occur at [REDACTED]-week intervals.

The safety of BIIB122 will be evaluated as follows:

Safety Cohort

[REDACTED]

[REDACTED]

CONFIDENTIAL

The information contained herein may not be used, disclosed, or published without the written consent of Biogen MA Inc.

[REDACTED]
[REDACTED]
[REDACTED]
(see [Figure 1](#)).

See [Appendix A](#) for details on procedures to follow in the event of a public health emergency.

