5.2. Study Duration for Participants

The total study duration for each participant (including the Screening period) will be a minimum of approximately 103 weeks and a maximum of approximately 187 weeks as follows:

- [REDACTED] Screening period [REDACTED]
 - [REDACTED] minimum to [REDACTED] maximum (when the total number of events for the primary endpoint reaches approximately [REDACTED] events) double-blind, placebo-controlled treatment period
 - [REDACTED] SFU period
- [REDACTED]
[REDACTED]
[REDACTED]

The study duration for each participant depends on the time point at which he or she enters the study and will be after both the last participant completes SFU (Week [REDACTED] + [REDACTED] weeks or [REDACTED] weeks after the last dose in case of early termination) and the minimum target number of primary endpoint events has been reached. Based on timing of last participant in and rate of primary endpoint events, sites will be contacted to schedule EOT and SFU for enrolled participants.

The EOT/ET Visit is a visit where assessments are performed for participants who either discontinue study treatment early or withdraw from the study. The EOT Visit is scheduled to align with a participant's last dose. If a participant discontinues study treatment but remains in the study, the EOT Visit will occur at the next scheduled visit. Participants who permanently discontinue study treatment early will be encouraged to continue study participation, maintaining the same schedule of study assessments as participants continuing in the double-blind treatment period. The ET Visit will occur if a participant withdraws from the study.

CONFIDENTIAL

The information contained herein may not be used, disclosed, or published without the written consent of Biogen MA Inc.

The end of study date for a participant may be the last study visit, last follow-up telephone conversation, or last protocol-specified assessment, or if the participant has ongoing AEs that are being followed, the date may be the date of AE resolution.

See [Figure 1](#) for a schematic of the study design.

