12.7. Methods of Analysis for Safety Endpoints

12.7.1. Adverse Events

AEs will be coded using the Medical Dictionary for Regulatory Activities. Any safety data collected from in-clinic or remote visits will be included in the statistical analysis.

All analyses of AEs will be based on the principle of treatment emergence. An AE is considered to be treatment emergent if it has an onset date on or after the date of first dosing, or if it was present prior to the first dose and subsequently worsened. Incidences of all AEs will be presented by system organ class and preferred term, by treatment group, and by visit. In addition, incidences of all AEs by severity, by relationship to study treatment [REDACTED]

will be presented. Data after participants started symptomatic PD medications will be analyzed both ways (included and excluded).

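### AEs and SAEs are summarised only as percentages of everyone dosed, so unequal study withdrawal between arms could understate a drug-related excess; person-time rates and Week 96 cumulative incidence should be added

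*Combined protocol and SAP*

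**What the plan says.** Section 4 of the protocol ties the safety objective to dosing over 96 to 180 weeks and gives it one endpoint: "Incidence of AEs and SAEs". Section 12.7.1 states how it is summarised: "Incidences of all AEs will be presented by system organ class and preferred term, by treatment group, and by visit". It adds breakdowns by severity and by relationship to treatment. Part of that last list is blacked out.

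Under Section 12.2 the safety set is every randomized participant with at least one dose, however long they were followed. An AE is treatment-emergent "if it has an onset date on or after the date of first dosing", or if it was present earlier and worsened. The readable text gives no closing date for that window, although Section 11.3.1 collects AEs from first dose to safety follow-up.

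Section 5.2 puts total participation at "a minimum of approximately 103 weeks and a maximum of approximately 187 weeks", depending on when the participant enters and when the event target is met. Section 8.1 encourages people who stop treatment to stay on the visit schedule. Section 8.3 ends participation for those who withdraw consent.

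Section 12.1 defers further detail to a SAP that overrides the protocol. No SAP text is in the document supplied.

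**The concern.** A percentage with an event depends on how long people were watched. If the arms are observed for different lengths of time, a comparison of percentages mixes the event rate with observation time. Leaving the study is an outcome that treatment can affect, through tolerability or efficacy, so randomization does not guarantee equal observation.

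Section 3.2.3 reports that both AE-related drug discontinuations in the 28-day Parkinson's study were in BIIB122 groups. Those are two treatment stops, not study withdrawals, and they prove nothing. They are still a reason not to take equal withdrawal for granted.

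Section 3.1.2 says the minimum treatment period is meant to extend the safety exposure data, and Section 3.3 puts earlier exposure in Parkinson's disease at 28 days. A muted excess would therefore matter here. The primary endpoint and two secondary efficacy endpoints handle the same varying follow-up as time to event. In the readable text, safety does not.

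**Working it through.** **The plan's own figure.** The synopsis gives a "5-week Screening period" and 96 to 180 weeks of treatment. Section 5.1 adds: "Each participant will have a SFU Visit 2 weeks after the last dose". So 5 + 96 + 2 = 103 weeks and 5 + 180 + 2 = 187 weeks, which reproduces Section 5.2. Observation after first dose is 98 to 182 weeks.

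**Assumptions.** The dropout rate is redacted and no AE rate is given. I assume:
- constant hazards for first event (λ) and withdrawal (d), independent of each other;
- d = −ln(1 − annual withdrawal);
- planned observation spread evenly over 98 to 182 weeks, that is a = 98/52.18 = 1.878 to b = 182/52.18 = 3.488 years;
- placebo λ = 0.05 per year and placebo withdrawal 5% per year.

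**Formula.** With k = λ + d, the expected percentage with an event is (λ/k) × [1 − (e^(−ka) − e^(−kb)) / (k(b − a))].

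- Placebo: d = 0.0513, k = 0.1013. (0.05/0.1013) × [1 − (0.8268 − 0.7024)/0.1631] = 11.7%.
- BIIB122, true ratio 1.5 (λ = 0.075), 15% withdrawal: d = 0.1625, k = 0.2375. (0.075/0.2375) × [1 − (0.6401 − 0.4367)/0.3824] = 14.8%. Ratio 1.26.
- BIIB122, no effect (λ = 0.05), 15% withdrawal: k = 0.2125. (0.05/0.2125) × [1 − (0.6709 − 0.4765)/0.3421] = 10.2%. Ratio 0.87.

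**Range, true ratio 1.5, placebo withdrawal 5% per year.**

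| BIIB122 annual withdrawal | Placebo | BIIB122 | Apparent ratio |
|---|---|---|---|
| 5% | 11.7% | 17.0% | 1.45 |
| 10% | 11.7% | 15.9% | 1.36 |
| 15% | 11.7% | 14.8% | 1.26 |
| 20% | 11.7% | 13.7% | 1.17 |
| 30% | 11.7% | 11.8% | 1.01 |

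The fall from 1.50 to 1.45 in the first row is the usual gap between a risk ratio and a rate ratio. The effect of unequal withdrawal at 15% is the further fall from 1.45 to 1.26. The excess drops from 5.3 to 3.1 points, or from about 11 to about 6 participants per 200.

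At placebo rates of 0.02 and 0.10 per year, 5% against 15% withdrawal gives 1.28 and 1.23. Hiding 1.5 completely needs about 30% to 31% annual withdrawal on BIIB122 across these rates. Hiding 1.25 needs about 19% to 20%.

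**The same case with person-time.** Mean time at risk at 5% against 15% is 122 and 103 weeks, or 2.34 and 1.97 years. Rates per 100 participant-years are 11.7/2.34 = 5.0 and 14.8/1.97 = 7.5, a ratio of 1.50. Cumulative incidence at Week 96 would be 1 − e^(−0.05 × 96/52.18) = 8.8% against 1 − e^(−0.075 × 96/52.18) = 12.9%, a ratio of 1.47. Both recover the excess because the model makes withdrawal independent of the event.

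**When the AE itself causes withdrawal.** Take 0.30 against 0.36 first AEs per year (true ratio 1.2), observation of 96 to 180 weeks, 5% background withdrawal in both arms, and 40% of BIIB122 participants leaving at their first AE. Total withdrawal on BIIB122 is then about 15% per year. Any-AE incidence is 57.5% against 51.2%, a ratio of 1.12, the same as with no extra withdrawal, because the AE is counted before the participant leaves. A separate event at 0.05 per year with a true ratio of 1.2 appears as 1.02 in percentages, while the person-time ratio is 1.20.

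**The case against.** Four stronger readings are tempting, and the documents do not support them.

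1. A reader might infer that the near-twofold range of follow-up biases the comparison. It does not. The range follows entry date and a common stopping rule, and 1:1 randomization balances both.

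2. A reader might infer that percentages distort even with equal follow-up, because the ratio shrinks for common events. At 0.3 per year, equal 5% withdrawal and 96 to 180 weeks, a true 1.3 appears as 60.3% against 51.2%, a ratio of 1.18. That is a correct comparison of risks with a 9.1-point excess in view. The compression is a property of the scale.

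3. A reader might infer that a drug causing both AEs and withdrawals would hide its own AEs. For the AE that prompts leaving, it would not, as the last calculation shows. The distortion falls on other or later events. That calculation also puts the AE-driven departures on BIIB122 alone, and the distortion would be smaller if placebo participants left in the same way.

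4. A reader might infer that the sponsor plans nothing else. That is not established. The word crude is not in the protocol, part of Section 12.7.1 is redacted, and the SAP is not supplied. The redaction does, however, fall within the list of relationship breakdowns.

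The design also limits the problem. Observation ends at leaving the study, not at stopping treatment. Section 8.3 asks for an early termination visit except after death or withdrawal of consent, and for remote safety follow-up where that visit cannot be done. An independent committee reviews safety data. By-visit incidences show timing, but no at-risk denominator is stated and they give no cumulative comparison.

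The assumed imbalance is large. At 15% and 5% per year, about 35% and 13% would have withdrawn by Week 138. The direction is not fixed either, since longer observation on BIIB122 would inflate an excess.

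**Conclusion.** The point holds in a limited form. As far as the text can be read, AEs and SAEs are summarised only as incidence among everyone dosed. If study withdrawal differs by arm, those percentages understate an excess, or show a false deficit, in the arm observed for less time. At 5% against 15% annual withdrawal and 0.05 events per year, a true 1.5 appears as about 1.26 and no effect as about 0.87. Complete masking of 1.5 needs about 30% per year on BIIB122, so the realistic risk is dilution of modest excesses.

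These sizes rest on assumed event and withdrawal rates, constant hazards, and withdrawal unrelated to the event. The finding concerns the main all-data tabulation and is conditional on the SAP. It is a worthwhile, inexpensive addition, and it does not make the planned percentages wrong.

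**What to change.** In Section 12.7.1, or in the SAP with a pointer from it, keep the percentages. For all AEs, SAEs, AESIs and AEs leading to discontinuation, add:

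- first-event rates per 100 participant-years, counting time from first dose to the first event or the end of AE observation (with that end stated), and the between-arm rate difference with a 95% confidence interval;
- cumulative incidence by arm at Week 96, which every participant is scheduled to reach;
- total observation time by arm.

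The cost is SAP wording and a few tables from dates already collected. No visit, dose or sample size changes. Rates assume a roughly constant hazard, which the Week 96 estimate offsets. Both measures assume withdrawal is non-informative, so they reduce the distortion but do not remove it if tolerability drives withdrawal. If the SAP already specifies these summaries, no change is needed.

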5. STUDY DESIGN

5.1. Study Overview

This Phase 3, multicenter, randomized, double-blind, placebo-controlled, parallel-group study is designed to evaluate the efficacy and safety of BIIB122 in approximately 400 participants with LRRK2-PD who are in the early stage of the disease. The study will be conducted at approximately 55 study sites globally. The study population is defined as participants with a clinical diagnosis of PD within 5 years of the Screening Visit, a mHY 1-2.5 (in OFF state), who carry a pathogenic variant in the LRRK2 gene (e.g., *G2019S*, *N1437H*, *R1441G*, *R1441C*, *R1441H*, *Y1699C*, or *I2020T*).

Randomization will be performed using IRT. Participants will be randomly assigned to receive BIIB122 225 mg or placebo orally QD in a 1:1 ratio. [REDACTED]

[REDACTED]

The double-blind placebo-controlled treatment period is a minimum of [REDACTED] weeks and could be as long as [REDACTED] weeks for each participant. The study duration depends on when the last enrolled participant has completed the [REDACTED] Visit and number of events for the primary endpoint reaches a minimum number to provide approximately [REDACTED] power for the study, which will be specified in the SAP, since the minimum number depends on the number, timing, and nature of planned interim analyses. Each participant will have a SFU Visit 2 weeks after the last dose. The majority of in-clinic visits occur at [REDACTED]-week intervals.

The safety of BIIB122 will be evaluated as follows:

Safety Cohort

[REDACTED]

[REDACTED]

CONFIDENTIAL

The information contained herein may not be used, disclosed, or published without the written consent of Biogen MA Inc.

[REDACTED]
[REDACTED]
[REDACTED]
(see [Figure 1](#)).

See [Appendix A](#) for details on procedures to follow in the event of a public health emergency.

5.2. Study Duration for Participants

The total study duration for each participant (including the Screening period) will be a minimum of approximately 103 weeks and a maximum of approximately 187 weeks as follows:

- [REDACTED] Screening period [REDACTED]
 - [REDACTED] minimum to [REDACTED] maximum (when the total number of events for the primary endpoint reaches approximately [REDACTED] events) double-blind, placebo-controlled treatment period
 - [REDACTED] SFU period
- [REDACTED]
[REDACTED]
[REDACTED]

The study duration for each participant depends on the time point at which he or she enters the study and will be after both the last participant completes SFU (Week [REDACTED] + [REDACTED] weeks or [REDACTED] weeks after the last dose in case of early termination) and the minimum target number of primary endpoint events has been reached. Based on timing of last participant in and rate of primary endpoint events, sites will be contacted to schedule EOT and SFU for enrolled participants.

The EOT/ET Visit is a visit where assessments are performed for participants who either discontinue study treatment early or withdraw from the study. The EOT Visit is scheduled to align with a participant's last dose. If a participant discontinues study treatment but remains in the study, the EOT Visit will occur at the next scheduled visit. Participants who permanently discontinue study treatment early will be encouraged to continue study participation, maintaining the same schedule of study assessments as participants continuing in the double-blind treatment period. The ET Visit will occur if a participant withdraws from the study.

CONFIDENTIAL

The information contained herein may not be used, disclosed, or published without the written consent of Biogen MA Inc.

The end of study date for a participant may be the last study visit, last follow-up telephone conversation, or last protocol-specified assessment, or if the participant has ongoing AEs that are being followed, the date may be the date of AE resolution.

See [Figure 1](#) for a schematic of the study design.

5.3. Study Stopping Rules

The Sponsor may terminate this study at any time, after informing Investigators. The Sponsor will notify Investigators and its partner when the study is to be placed on hold, completed, or terminated. Study drug administration may be terminated by the Sponsor at the recommendation of the IDMC based exclusively on safety and tolerability data, or at the discretion of the Sponsor.

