7.4. Blinding Procedures

The Investigator, Sponsor, study staff, and participants will remain blinded to the treatment assignments. To maintain the study blind, it is imperative that treatment assignments are not shared with the participants, their families, or any member of the blinded study team, at the site, Sponsor, and CRO.

At the end of the study (i.e., once the clinical study report is finalized), if unblinding will not jeopardize the results of ongoing related studies, the Sponsor will provide the randomization codes to Investigators, who then can inform their participants about the treatment received.

In the event of a medical emergency that requires unblinding of a participant's treatment assignment, refer to Section 11.4.3.

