12.9. Interim Analyses

Up to 2 IAs, one earlier and one later in the study, pending regulatory feedback, may be performed for efficacy over the course of the study. A Lan-Demets alpha-spending function will be used to approximate the O'Brien Fleming for the interim and final analysis, to control the overall type I error alpha level at 0.05 two-sided. Additional details will be described in the SAP.

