14.3. Study Committees

14.3.1. Advisory Committee

An advisory committee will be formed to provide scientific and medical direction for the study and to oversee the administrative progress of the study. The advisory committee will meet at least annually to monitor participant accrual and to monitor compliance with the protocol at individual study sites. The advisory committee will be blinded to participant treatment assignments.

Members of the advisory committee will include the Medical Director, Clinical Operations Lead, Clinical Trial Lead, and Project Statistician from the Sponsor, and participating key opinion leaders. The Sponsor will designate one of the participating key opinion leaders to be the chairperson of the advisory committee.

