14.3.2. Independent Data Monitoring Committee

An IDMC will monitor accumulating participant safety data during the study [REDACTED]

[REDACTED]. A dedicated safety data review for the Safety Cohort will be conducted by the IDMC approximately [REDACTED] weeks after the [REDACTED] participant is randomized and dosed, to evaluate the appropriateness of the protocol safety monitoring procedures. The role and responsibilities of the IDMC and further details will be included in the IDMC Charter.

CONFIDENTIAL

The information contained herein may not be used, disclosed, or published without the written consent of Biogen MA Inc.

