APPENDIX B. SAFETY MONITORING PLAN

■■■■■ Serious Adverse Events

-
-
-

-

-

-

■■■■■

[figure not shown]
CONFIDENTIAL

The information contained herein may not be used, disclosed, or published without the written consent of
Biogen MA Inc.

[figure not shown]
CONFIDENTIAL

The information contained herein may not be used, disclosed, or published without the written consent of
Biogen MA Inc.
98

[figure not shown]
CONFIDENTIAL

The information contained herein may not be used, disclosed, or published without the written consent of
Biogen MA Inc.

[figure not shown]
CONFIDENTIAL

The information contained herein may not be used, disclosed, or published without the written consent of
Biogen MA Inc.
100

[figure not shown]
CONFIDENTIAL

The information contained herein may not be used, disclosed, or published without the written consent of
Biogen MA Inc.

[figure not shown]
CONFIDENTIAL

The information contained herein may not be used, disclosed, or published without the written consent of
Biogen MA Inc.

CONFIDENTIAL

The information contained herein may not be used, disclosed, or published without the written consent of
Biogen MA Inc.

Independent Data Monitoring Committee

[figure not shown]
[figure not shown]
An IDMC will monitor accumulating participant safety data during the course of the study as described in Section 14.3.2 of the protocol.

CONFIDENTIAL

The information contained herein may not be used, disclosed, or published without the written consent of
Biogen MA Inc.

[figure not shown]
CONFIDENTIAL

CONFIDENTIAL

[figure not shown]
CONFIDENTIAL

The information contained herein may not be used, disclosed, or published without the written consent of
Biogen MA Inc.

CONFIDENTIAL

The information contained herein may not be used, disclosed, or published without the written consent of
Biogen MA Inc.

CONFIDENTIAL

The information contained herein may not be used, disclosed, or published without the written consent of
Biogen MA Inc.

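### Does limiting an IDMC stopping recommendation to safety data (Section 5.3) conflict with the efficacy interims allowed in Section 12.9?

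*Combined protocol and SAP*

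**What the plan says.** Section 5.3 of the protocol gives two routes to ending study drug. Its wording for this is: "terminated by the Sponsor at the recommendation of the IDMC based exclusively on safety and tolerability data, or at the discretion of the Sponsor". At study level, the same section adds: "The Sponsor may terminate this study at any time, after informing Investigators".

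Section 12.9 states: "Up to 2 IAs, one earlier and one later in the study, pending regulatory feedback, may be performed for efficacy". It specifies Lan-DeMets spending of O'Brien-Fleming type at an overall two-sided 0.05 and refers further detail to the SAP. It names no reviewing body and no action on a crossing.

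On blinding, Section 7.4 says: "The Investigator, Sponsor, study staff, and participants will remain blinded to the treatment assignments". Its next sentence speaks of the blinded study team at site, Sponsor and CRO.

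On committees, Section 14.3.2 begins: "An IDMC will monitor accumulating participant safety data during the study". The sentence then runs into a redaction, and the section assigns the committee's role to the IDMC Charter. Appendix B refers back: "An IDMC will monitor accumulating participant safety data during the course of the study as described in Section 14.3.2 of the protocol". Section 14.3.1 sets up a separate advisory committee: "Members of the advisory committee will include the Medical Director, Clinical Operations Lead, Clinical Trial Lead, and Project Statistician from the Sponsor". Of that committee it says: "The advisory committee will be blinded to participant treatment assignments".

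**The concern.** An efficacy interim is useful only if someone unblinded reads it and can pass on a recommendation. On the visible text, the IDMC is described as a safety committee, and its recommendation to end study drug is tied to safety and tolerability alone. The advisory committee is blinded and includes the Sponsor's Project Statistician. The only Sponsor unblinding described is for SUSARs (Section 11.3.5). What remains is Sponsor discretion, held by a party that Section 7.4 keeps blind.

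The stake would be trial integrity. If access were settled only after a boundary was crossed, the Sponsor might see unblinded efficacy while still maintaining the SAP (Section 12.1). That SAP is to fix the minimum number of primary events (Section 5.1).

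**Working it through.** **1. The sections side by side**

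| Question | Visible text | Conflict? |
|---|---|---|
| Can the IDMC recommend ending study drug on efficacy? | Section 5.3: its recommendation rests on safety and tolerability only | A limit on one route |
| Can study drug or the study be ended for another reason? | Section 5.3: yes, at Sponsor discretion, with no stated basis required | No |
| Must a crossed boundary end study drug? | Section 12.9: no action stated | No |
| Must the Sponsor see unblinded data to act? | Not stated; a report that a boundary was crossed would be enough | No |
| Who reviews interim efficacy? | Section 12.9 refers to the SAP, Section 14.3.2 to the Charter; part of 14.3.2 is redacted | Not determinable from this text |

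A contradiction would need one passage to require what another forbids, and none does. A Sponsor stop after a crossing complies with Section 5.3.

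**2. Type I error**

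Under the null hypothesis, the probability of crossing at any look is 0.05 two-sided by construction. Ignoring an interim crossing and testing only at the final boundary lowers the error to the final nominal level. In the six settings below that level is 0.0392 to 0.0463. Uncertainty over who may act on a crossing therefore cannot push the error above 0.05.

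**3. Power and the chance of a crossing**

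Inputs:
- 200 events (Section 1.1, Duration of Study Participation).
- 1:1 allocation (Section 5.1).
- Two-sided 0.05 (Section 12.9).
- Hazard ratio 0.65. This is an assumption that reads the 35% in Section 3.1.2 as a hazard reduction, because the hazard ratio in Section 12.10 is redacted.
- Look times. These are also assumed, since none is visible.

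Drift = −ln(0.65) × √(200/4) = 0.4308 × 7.071 = 3.046. Power with no interim = Φ(3.046 − 1.960) = Φ(1.086) = 86.1%. The plan's own power figure is redacted, so it cannot be reproduced.

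The spending function is 2[1 − Φ(z/√t)], where t is the fraction of events. For spending on the total 0.05, z = 1.960. For spending 0.025 on each side, z = 2.241 and the result applies to each side. Boundaries come from numerical integration.

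| Looks (fraction of events) | Spending | Crossed by look 2 | Overall power | Final nominal p |
|---|---|---|---|---|
| 1/3, 2/3 | total 0.05 | 53.3% | 85.4% | 0.0439 |
| 0.50, 0.75 | total 0.05 | 63.9% | 85.1% | 0.0411 |
| 0.60, 0.80 | total 0.05 | 69.3% | 84.9% | 0.0392 |
| 1/3, 2/3 | 0.025 per side | 49.1% | 85.7% | 0.0463 |
| 0.50, 0.75 | 0.025 per side | 61.3% | 85.5% | 0.0440 |
| 0.60, 0.80 | 0.025 per side | 67.6% | 85.3% | 0.0423 |

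The looks cost 86.1 − 85.7 = 0.4 to 86.1 − 84.9 = 1.2 points of power. If neither look were acted on, final-test power would be 83.7% to 85.4%.

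If the 35% is instead read as a longer median time, the hazard ratio is about 1/1.35 = 0.74. The drift is then 2.129, and the chance of crossing by look 2 is 22% to 38%.

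**The case for a change.** The strongest opposing case is that Section 5.3 is not redacted and its limiting word is deliberate. If the Charter gives the IDMC an efficacy role, Section 5.3 appears to deny it the matching recommendation. If the Charter does not, no visible body reviews the interim. The SAP-override clause in Section 12.1 is written for statistical methods and may not reach decision authority or blinding. Conditional interims are no defence either, because access rules have to be in place before the first look.

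Part of this stands. The sections are not aligned, and a reader cannot trace from Section 5.3 what follows a crossing.

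The two-way choice fails, though. The Charter could have the IDMC, or an independent statistician, review efficacy and report only that the boundary was met, leaving the Sponsor to decide under its own discretion. Section 5.3 restricts the basis for one kind of recommendation. It does not say who may conduct or communicate an interim. Section 7.4's reference to a blinded team is also compatible with separate unblinded staff, although none is described.

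The feared harm needs several steps in a row: interims adopted, Charter and SAP both silent, access improvised, and SAP control then misused. Section 5.1 makes the minimum event number depend on the planned interims, which suggests it is set with the interim plan and not after results are seen.

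**Conclusion.** No change to the plan is called for. Sections 5.3, 7.4 and 12.9 are loosely joined but compatible. The missing detail lies where the plan says it will be supplied, in the SAP and the IDMC Charter, or behind the redaction in Section 14.3.2, which cannot be counted as an omission. A cross-reference from Section 5.3 would be tidy if interims are adopted, but it would alter neither an analysis nor a conclusion.

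The effect on type I error is nil. The power cost of 0.4 to 1.2 points belongs to the interim looks, not to the wording of Section 5.3. The crossing probabilities (49% to 69% at a hazard ratio of 0.65, 22% to 38% at 0.74) rest on assumed effects and look times. They show only that a crossing is a realistic event if interims are held.

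This conclusion assumes that the Charter and SAP name, before any look, who sees interim efficacy and how a recommendation reaches a blinded Sponsor. Neither is in the text reviewed. If both proved silent, the governance question would be open again.
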